6.2.3 Analysis of Unsolicited AE

All unsolicited AEs and MAAE recorded in the CRF will be mapped to preferred terms using the most recent MedDRA dictionary and classified by System organ class (SOC) and Preferred Terms (PT). Under the classification standard of MedDRA terms, and all AEs excluding the AEs whose causal relation with the study medication is ‘Not Related’ shall be treated as AEs whose causal relation cannot be excluded {hereafter “Adverse Drug Reaction(ADR)”}.

- ① The frequency and percentage of unsolicited AE (Day 1-7) and MAAE (Day 1-29) according to the expected, serious, severity, frequency, action taken, outcome, relationship to MenACWY-CRM regarding occurred AE will be calculated.
- ② The frequency of unsolicited AEs (Day 1-7) and MAAE (Day 1-29) will be classified into the preferred terms according to the expected, serious, severity, frequency, action taken, outcome, relationship to MenACWY-CRM.
- ③ The number of subjects and percentage of SAE/Serious ADR (SADR), unexpected AE/ADR,

	CONFIDENTIAL :	Last Update Date
	THIS DOCUMENT AND INFORMATION CONTAINED HEREIN IS PROPRIETARY TO COMPANY AND IS NOT TO BE DISCLOSED WITHOUT THE WRITTEN PERMISSION OF COMPANY.	20-APR-2018
STATISTICAL ANALYSIS PLAN(V6.0)		

MAAE/ADR, unsolicited AE/ADR and continuous solicited AE/ADR will be calculated according to the preferred terms. And the number of subjects and percentage by study vaccination number of SAE/Serious ADR (SADR), unexpected AE/ADR, MAAE/ADR, unsolicited AE/ADR and continuous solicited AE/ADR will be calculated according to the preferred terms in infants 2 to 23 months.

- ④ For subjects excluded from safety per protocol set[†], the number of subjects and the percentage of SAE/Serious ADR (SADR), unexpected AE/ADR, MAAE/ADR, unsolicited AE/ADR and continuous solicited AE/ADR will be calculated according to the preferred terms. And the number of subjects and percentage by study vaccination number of SAE/Serious ADR (SADR), unexpected AE/ADR, MAAE/ADR, unsolicited AE/ADR and continuous solicited AE/ADR will be calculated according to the preferred terms in infants 2 to 23 months.

[†] Subject excluded from safety per protocol set: Except for subjects who didn't receive study vaccination and follow-up failure.

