7.6.3 Analysis of Other Adverse Events

All the unsolicited AE occurring from Day 1 to Day 7, and medically attended AE occurring from Day 1 to Day 29 judged either as related to vaccination or not by the investigator, will be recorded as specified in section 6.2.5. The original verbatim terms used by investigators to identify adverse events in the CRFs will be mapped to preferred terms using the most recent MedDRA dictionary. The AEs will then be grouped by

MedDRA preferred terms into frequency tables according to system organ class. All reported adverse events, as well as adverse events judged by the investigator as at least possibly related to study vaccine, will be summarized according to system organ class and preferred term within system organ class. When an AE occurs more than once for a subject, the maximal severity and strongest relationship to the vaccine group will be counted. Additionally, three separate summaries will be produced: (i) serious adverse events, (ii) medically attended adverse events that are possibly or probably related to vaccine, and (iii) adverse events that are possibly or probably related to vaccine. Data listings of all adverse events will be provided by subject. In addition, a listing of subjects withdrawn from the study because of an adverse event will be presented.

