5.1 Safety Set

Table 5.1.1 Summary of Unsolicited AE

Safety Set		2-23 months		2-10		11-18		19-34		35-55		≥ 56		Total	
		No. AEs	(%)	No. AEs	(%)	No. AEs	(%)	No. AEs	(%)	No. AEs	(%)	No. AEs	(%)	No. AEs	(%)
Expected	Expected AE														
	Unexpected AE														
Serious	Yes														
	No														
Severity	Mild														
	Moderate														
	Severe														
Frequency	Single/Continuous														
	Intermittent														
Action Taken	None														
	Uncertain														
	Procedure or physical therapy														
	Blood or blood products														
	Withdrawn from study due to AE														
	Prescription drug therapy														

Safety Set		2-23 months	2-10	11-18	19-34	35-55	≥ 56	Total
		No. AEs (%)						
	Non-prescription drug therapy Hospitalization IV fluids Physician visit Other							
Outcome	Complete recovery/Return to baseline Alive with sequelae Death Unknown/Lost to follow-up AE persisting							
Relationship to study vaccine	Not related Possibly related Probably related							
Total								

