2.2 Number of Subjects

A total of approximately 3,960 subjects are planned for enrolment into this study.

Assuming a 10% drop-out rate, this should provide approximately 3,000 evaluable subjects in the cohort 2 to 55 years of age and 600 in the cohort 2 to 23 months of age. This sample size meets the post-licensure requirements of the MFDS to provide continued safety monitoring in the Korean population.

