4.1 Safety Endpoints

Safety will be assessed after administration of study vaccine in terms of the number and percentage of subjects with:

- Local and systemic solicited adverse events reported from study Day 1 (day of vaccination) through study Day 7 post-vaccination;
- Unsolicited AEs reported from study Day 1 (day of vaccination) through study Day 7 post-vaccination;
- Medically attended AEs reported from study Day 1 to study termination (Day 29/early termination);
- SAEs reported from study Day 1 to study termination (Day 29/early termination).

5. Assessment Criteria

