6.2.2. Analysis of Solicited AE

Frequencies and % of subjects experiencing each adverse event will be presented for each symptom severity. Summary tables showing the occurrence of any local or systemic reaction overall and at each time point will also be presented (see Appendix 1 Table 4.1.3 and 4.2.3).

Post-vaccination adverse events reported from Day 1 to Day 7 will be summarized by maximal severity. The severity of local adverse events for subjects < 6 years of age will be categorized as follows. Injection-site erythema and induration: absent (0 to 9 mm), mild (10 to 25 mm), moderate (26 to 50 mm), severe (> 50 mm); injection-site tenderness: none, mild (minor light reaction to touch), moderate (cried or protested to touch), severe (cried when injected limb was moved). For subjects \geq 6 years, injection-site erythema and induration absent (1 to 24 mm), mild (25 to 50 mm), moderate (51 to 100 mm), severe (>100 mm); pain: none, mild (present but does not interfere with activity), moderate (interferes with activity), severe (prevents daily activity).

For subjects \geq 6 years of age, the severity of systemic adverse events (i.e., chills, nausea, malaise, generalized myalgia, generalized arthralgia, headache) occurring up to 7 days after each vaccination will be categorized as none, mild (present but not interfering with daily activity), moderate (some interference with daily activity), and severe (prevents daily activity) except for rash, which will be

	CONFIDENTIAL :	Last Update Date
	THIS DOCUMENT AND INFORMATION CONTAINED HEREIN IS PROPRIETARY TO COMPANY AND IS NOT TO BE DISCLOSED WITHOUT THE WRITTEN PERMISSION OF COMPANY.	20-APR-2018
STATISTICAL ANALYSIS PLAN(V6.0)		

categorized as none, urticarial, or other.

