7.3 Safety Analyses

- Incidence proportion and the number of AEs according to the baseline characteristics (frequency and percentage).
- The number of the expected serious, severity, frequency, action taken, outcome, relationship to MenACWY-CRM for Unsolicited AE (DAY 1-7) and MAAE (DAY 1-29) (frequency and percentage).
- The number of AEs for the severity, day, fever to MenACWY-CRM according to individual solicited AE (DAY 1-7) (frequency and percentage).
- Incidence proportion and number according to the preferred terms of SAE/SADR, unexpected AE/ADR, MAAE/ADR, unsolicited AE/ADR and continuous solicited AE/ADR (frequency and percentage)
- For subjects excluded from safety per protocol set[†] incidence proportion and number according to the preferred terms of SAE/SADR, unexpected AE/ADR, MAAE/ADR, unsolicited AE/ADR and continuous solicited AE/ADR (frequency and percentage).

	CONFIDENTIAL :	Last Update Date
	THIS DOCUMENT AND INFORMATION CONTAINED HEREIN IS PROPRIETARY TO COMPANY AND IS NOT TO BE DISCLOSED WITHOUT THE WRITTEN PERMISSION OF COMPANY.	20-APR-2018
STATISTICAL ANALYSIS PLAN(V6.0)		

† Subject excluded from safety per protocol set: Except for subjects who didn't receive study mediation and follow-up failure.

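### Severity of unsolicited and medically attended AEs is tabulated by event only, so the SAP gives no number or percentage of subjects with a severe one

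*SAP*

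**What the plan says.** SAP V6.0, 6.2.3, item 1 calls for "The frequency and percentage of unsolicited AE (Day 1-7) and MAAE (Day 1-29) according to the expected, serious, severity", then frequency, action taken, outcome and relationship. Item 2 repeats this by preferred term, with frequencies only. The matching entry in 7.3 is also a plain count by attribute.

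Items 3 and 4 of the same section use a different unit: "The number of subjects and percentage of SAE/Serious ADR (SADR), unexpected AE/ADR", followed by MAAE/ADR, unsolicited AE/ADR and continuous solicited AE/ADR, all by preferred term. None of these is split by severity.

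The latest shells supplied are in the V4.0 Appendix 1. Table 5.1.1, "Summary of Unsolicited AE", and Tables 5.2.1, 6.1.1 and 6.2.1 have columns for the number of AEs with a percentage. None has a column for subjects.

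Solicited AEs are handled differently. SAP 6.2.2 says "Frequencies and % of subjects experiencing each adverse event will be presented for each symptom severity" and summarises them by maximal severity. Protocol 7.6.3, on other adverse events, says "When an AE occurs more than once for a subject, the maximal severity and strongest relationship to the vaccine group will be counted".

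**The concern.** A reader of a vaccine safety report wants to know what fraction of vaccinees had a severe unsolicited or medically attended event. A share of events does not answer that. Repeated mild events in some subjects pull the severe share down, and a recurring severe event in one subject pushes it up. Repeats are also built into the design: infants may be followed after several study vaccinations, and study vaccination number runs from 1 to 4. As planned, severity would be on a subject scale for solicited AEs and on an event scale for unsolicited AEs and MAAEs, and the two could not be compared.

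**Working it through.** **1. The plan's own figure.** SAP 2.2 states "A total of approximately 3,960 subjects are planned for enrolment into this study", with 10% drop-out and 3,000 + 600 = 3,600 evaluable. Check: 3,600 × 1.1 = 3,960, and 3,960 × 0.9 = 3,564, within about 1% of 3,600. This only supplies a subject denominator; the documents give no AE counts.

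**2. Which unit is used where.**

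- 6.2.3 item 1 and the 7.3 entry: AEs by attribute; subjects are not mentioned.
- 6.2.3 items 3 and 4: subjects, by preferred term, without severity.
- V4.0 Tables 5.1.1, 5.2.1, 6.1.1 and 6.2.1: number of AEs (%), including the severity rows.
- V4.0 Table 2.1.1: subjects with any unsolicited AE, SAE or MAAE, without severity.
- 6.2.2: subjects by maximal severity, for solicited AEs only.

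Item 1 does not name its denominator. The event reading rests on the contrast with item 3 and on the shells. V1.0 to V3.0 use the same unit as V4.0. The V5.0 and V6.0 shells are not supplied, but the V6.0 revision log reports no change of unit: for 6.2.3 it lists a change to the MAAE criteria, besides general wording edits.

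**3. Can an event share be turned into a subject risk?** Let E be the number of events, s the severe share and N the number of subjects. The subjects with at least one severe event number between 1 and s × E, so the subject percentage lies between 1/N and sE/N. With N = 3,600 and an assumed s = 5%:

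| E (assumed) | Severe events | All in one subject | All in different subjects |
|---|---|---|---|
| 200 | 10 | 1/3,600 = 0.03% | 10/3,600 = 0.28% |
| 500 | 25 | 0.03% | 25/3,600 = 0.69% |
| 1,000 | 50 | 0.03% | 50/3,600 = 1.39% |

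**4. The reverse direction.** Assume that 300 of 3,600 subjects have an unsolicited AE and 30 of them have a severe one. The subject results are then fixed: 30/3,600 = 0.83% of all subjects and 30/300 = 10% of subjects with an AE. The event share still moves:

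- Each severe subject has one event and the other 270 average k events, so the share is 30/(30 + 270k). For k = 1.2, 1.5 and 2 this is 30/354 = 8.5%, 30/435 = 6.9% and 30/570 = 5.3%.
- Each severe subject has r severe events and the others have one, so the share is 30r/(30r + 270). For r = 2 and 3 this is 60/330 = 18.2% and 90/360 = 25.0%.

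The like-for-like comparison is with 10%, not 0.83%. The two patterns put the repeats in one group only, so they mark out a range and do not predict a value.

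**The case against.** Several stronger readings are tempting, and the documents do not support them.

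- *The SAP contradicts its own endpoints.* Section 4.1 says "Safety will be assessed after administration of study vaccine in terms of the number and percentage of subjects with" and then lists solicited AEs, unsolicited AEs, MAAEs and SAEs. Severity is not part of any endpoint. The endpoints are delivered by subject in 6.2, Table 2.1.1 and item 3.
- *Every attribute lacks a subject count.* Seriousness, expectedness and relationship (as ADR) have one in item 3. Frequency, action taken and outcome are recorded per event, and tabulating them by event is natural.
- *The protocol counts each subject once.* Its rule concerns an AE that recurs within a subject, not all of a subject's AEs together. Protocol 7.6.3 also lists no severity table for unsolicited AEs, so the SAP has not dropped a named output.
- *The denominator is wrong.* A share of events, labelled as such, is a legitimate descriptive figure.

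Two further points weaken the case. Amendment 2 assigns the protocol's statistical section to ICH reporting and makes the MFDS plan a separate document, so not repeating a protocol rule is not clearly a contradiction, and an ICH report might still apply it. The full protocol text supplied is also the original version; the amendments list section 7 or 7.6 among those changed. Finally, Protocol 7.6.3 promises AE listings by subject, so the missing count could be recovered by hand.

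All of this stands. It narrows the point to severity and to this SAP. It does not supply the missing number.

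**Conclusion.** The point holds for severity. In SAP V6.0, read with the latest supplied shells, severity of unsolicited AEs and MAAEs is summarised by event only, and subjects with a severe event are not counted. That is out of step with the SAP's own handling of solicited AEs and with the protocol's maximal-severity rule. It is a reporting gap, not a conflict with the endpoints, and worth closing because the remedy is nearly free.

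Its size cannot be stated from the documents. The illustrations show only that an event share does not determine a risk per vaccinee: under assumed counts, one event share fits subject percentages up to 50-fold apart (1 against 50 subjects, at 1,000 events), and one subject result fits event shares from 5.3% to 25.0%. The conclusion assumes that the unit did not change in the V5.0 and V6.0 shells. That no subject count exists is shown for this SAP only, not for every report of the study.

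**What to change.** - Add a column of subjects, n (%), to the severity part of the unsolicited AE and MAAE tables (5.1.1, 5.2.1, 6.1.1 and 6.2.1 in the V4.0 numbering) and to the text of 6.2.3 items 1 and 2. The denominator is the Safety Set, or the Safety per protocol set in the matching tables.
- Count each subject once at maximal severity overall and once per SOC and preferred term. The preferred-term count applies Protocol 7.6.3 directly; the overall count extends it.
- State that infants followed after more than one study vaccination are counted once overall and once per vaccination number.
- Keep the event counts and percentages, labelled as shares of events.

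The cost is one derived variable and one extra column. Severity is already collected, so no new data are needed.

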6.3 Additional Analyses for DDS (Data Disclosure Shell)

The following will be presented in the Safety set and Safety per Protocol set.

- Frequency and percentage by Age group (2-23 months, 2-10, 11-18, 19-64) will be presented.
- Frequency and percentage by study termination and reason not completed will be presented.
- The number of subjects of Non-SAE and the number of Non-SAE incurred shall be calculated, the incidence proportion of Non-SAE and its 95% confidence interval will be calculated using the normal approximation.
- The number of death resulting from AE shall be calculated.
- The number of subjects and percentage of Non-SAE will be calculated according to the preferred terms.

6.4 Additional Analyses for AE in the Local Product Label (Unsolicited AE Day 1-29)

The following will be presented in the Safety set and Safety per Protocol set.

- Preferred terms of Serious AE/ADR, unexpected AE/ADR will be presented respectively according to the proportion of AE in the local product label.

	CONFIDENTIAL :	Last Update Date
	THIS DOCUMENT AND INFORMATION CONTAINED HEREIN IS PROPRIETARY TO COMPANY AND IS NOT TO BE DISCLOSED WITHOUT THE WRITTEN PERMISSION OF COMPANY.	20-APR-2018
STATISTICAL ANALYSIS PLAN(V6.0)		

7. List of Table and Data Listings

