7.3 Population for Analysis

Definition of populations to be analyzed:

(a) All Enrolled Set

All subjects who have signed an informed consent form, undergone screening procedure(s) and received a subject number.

(b) Exposed Set

All subjects in the enrolled set who receive a study vaccination.

(c) Safety Set

All subjects in the Exposed set who provide post vaccination safety data.

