3.1 Safety Analysis Sets

Safety Set

All subjects who

- have signed an informed consent form, undergone screening procedure(s) and received a subject number,
- received a study vaccination,
- provided post vaccination safety data.

Safety per protocol set

All subjects in the safety Set with the exclusions of the following cases:

- (1) Subjects administered prior to the contract date.
- (2) Subjects who didn't receive MenACWY-CRM.
- (3) Follow-up failure: The subjects whose safety information cannot be identified due to follow-up loss.
- (4) Not applicable to the indication of study drug
[Indication]
- To prevent invasive meningococcal disease caused by Neisseria meningitides serogroups A, C, Y and W-135 in persons 2 months through 55 years of age.
- (5) Subjects who violate of Protocol: Those who do not meet one item at least of the inclusion/exclusion criteria.
[Inclusion criteria]
 - 1) Male and female subjects from 2 months to 55 years of the age at the time of Visit 1 (including all 55 years old subjects, up to one day before their 56th year birthday), who are scheduled to receive vaccination with MenACWY-CRM conjugate vaccine, according to the local prescribing information and routine clinical practice.
 - 2) To whom the nature of the study has been described and the subject or subject's parent/legal representative has provided written informed consent.
 - 3) Whom the investigator believes that the subject can and will comply with the requirements of the protocol.
 - 4) Who are in good health as determined by the outcome of medical history, physical

	CONFIDENTIAL :	Last Update Date
	THIS DOCUMENT AND INFORMATION CONTAINED HEREIN IS PROPRIETARY TO COMPANY AND IS NOT TO BE DISCLOSED WITHOUT THE WRITTEN PERMISSION OF COMPANY.	20-APR-2018
STATISTICAL ANALYSIS PLAN(V6.0)		

assessment and clinical judgment of the investigator.

[Exclusion criteria]

- 1) Contraindication, special warnings and/or precautions, as evaluated by the investigators, reported in the MenACWY-CRM conjugate vaccine Korean prescribing information
 - 2) Infants who were already enrolled in this trial for previous vaccination.
- (6) Subjects who prescribed off-label dosage:
- Vaccine schedule for children from 2 to 23 months of age :

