 - Infants 2 to 6 months of age : Three doses of MenACWY-CRM, each of 0.5 ml, is to be given with an interval of at least 2 months; the fourth dose schedule be administered during the second year of life with an interval of at least 6 months after the third dose.
 - Infants 7 to 23 months of age : MenACWY-CRM is to be administered as two doses, each as single dose (0.5ml), with the second dose administered in the second year of life and at least three months after the first dose.
 - 2 to 55 years of age : MenACWY-CRM is to be administered as a single dose (0.5ml).
 - * The infant from 2 to 23 months of age may enroll at any point, in the vaccination series, including those subjects who may already initiated vaccination series. According to parental consents, these subjects may be followed up for 29 days within the surveillance period after subsequent vaccination(s) at the same study site.

Non-Safety per protocol set

Subjects excluded from safety per protocol set except for subjects who did not receive MenACWY-CRM and follow-up failure.

Based on rules for estimation of each number of safety evaluation cases, the following local regulation and Guideline on Standards for re-examination for new drugs, etc of MFDS, non-safety analysis set are excluded from the safety analysis set:

Guideline on Standards for re-examination for new drugs, etc (Chapter II, no. 3)

Patient Population for Surveillance:

- A) Patients planned to receive a drug under surveillance by investigator's medical judgment shall be subject.
- B) Subject who do not use within approved range shall not be included in the subject in principal.

However, if data of subject whose use is beyond approved range is collected, perform analysis as a separate item.

	CONFIDENTIAL :	Last Update Date
	THIS DOCUMENT AND INFORMATION CONTAINED HEREIN IS PROPRIETARY TO COMPANY AND IS NOT TO BE DISCLOSED WITHOUT THE WRITTEN PERMISSION OF COMPANY.	20-APR-2018
STATISTICAL ANALYSIS PLAN(V6.0)		

C) Describe actual selection methods of subject in detail.

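### SAP V6.0 tabulates study completion and reasons for non-completion only in sets that require safety data, so subjects lost without such data disappear from the table and non-completion is understated by an unknown amount

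*SAP*

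**What the plan says.** SAP V6.0 section 6.3 opens with the populations for all its items: "The following will be presented in the Safety set and Safety per Protocol set". Its second item is the disposition table: "Frequency and percentage by study termination and reason not completed will be presented". Section 7.4 lists the same output and names no other population.

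Section 3.1 defines the sets. Entry to the Safety set requires, besides consent and vaccination, that the subject "provided post vaccination safety data". The Safety per protocol set is a subset of it, and one of its exclusions is "Follow-up failure: The subjects whose safety information cannot be identified due to follow-up loss". The remaining set is described as "Subjects excluded from safety per protocol set except for subjects who did not receive MenACWY-CRM and follow-up failure".

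Protocol 7.3 has two wider sets. The All Enrolled Set is "All subjects who have signed an informed consent form, undergone screening procedure(s) and received a subject number", and the Exposed Set is the vaccinated part of it. SAP V6.0 section 3.1 carries neither.

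SAP section 7.1 reports how many subjects were contracted, how many completed CRFs came back and how many subjects are in the safety population. It gives no reasons for non-completion.

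On the data side, Protocol 3.3 has study termination completed on the CRF for every subject, and Protocol 3.3.1 lists reasons for early termination among the items collected.

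**The concern.** A disposition table shows how many of those who started reached the end, and why the others did not. Here the denominator is conditioned on having safety data, so the subjects of most interest, those who left nothing behind, are removed before the table is built. They are in none of the SAP's three sets, so no other table in the plan reports their reasons.

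This is a single-arm, descriptive safety study. Its Day 1 to 29 results on medically attended and serious adverse events are simple proportions, and how far they can be trusted depends on how complete follow-up was and whether losses might relate to tolerability. A table restricted to subjects with data cannot show that. Section 8 sends the section 6.3 output to the re-examination report, so the regulator would be one of its readers.

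**Working it through.** **The plan's own figure.** SAP 2.2 states: "A total of approximately 3,960 subjects are planned for enrolment into this study". It continues: "Assuming a 10% drop-out rate, this should provide approximately 3,000 evaluable subjects in the cohort 2 to 55 years of age", with a further 600 aged 2 to 23 months, hence about 3,600 evaluable.

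- Forward: 3,960 × (1 − 0.10) = 3,564, against 3,600; the gap of 36 is 1.0%.
- Backward: 1 − 3,600/3,960 = 9.1%.

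The figure reproduces within rounding.

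**Where each kind of drop-out goes** (SAP 3.1, Protocol 7.3):

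| Subject | All Enrolled | Exposed | Safety | Safety per protocol | Non-Safety per protocol |
|---|---|---|---|---|---|
| Enrolled, not vaccinated | yes | no | no | no | no |
| Vaccinated, lost, no safety data | yes | yes | no | no | no |
| Vaccinated, left early, some safety data | yes | yes | yes | yes, unless excluded for another reason | only if excluded for another reason |

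The first two rows are invisible to section 6.3. The third row is counted as not completed in the Safety set, and in the per-protocol set as well unless another exclusion applies, because early termination, consent withdrawal and withdrawal for an adverse event are not per-protocol exclusions.

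**Size.** Let d be the true share of enrolled subjects who do not complete and f the share of those who have no post-vaccination safety data. The Safety set then shows

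non-completion = d(1 − f) / (1 − d·f).

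I take d = 0.10 from the drop-out allowance (0.10 × 3,960 = 396 subjects). The documents do not give f, so its whole range is shown:

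| f | Non-completers in table | Safety set size | Shown | All Enrolled |
|---|---|---|---|---|
| 0 | 396 | 3,960 | 10.0% | 10.0% |
| 0.25 | 297 | 3,861 | 7.7% | 10.0% |
| 0.50 | 198 | 3,762 | 5.3% | 10.0% |
| 0.75 | 99 | 3,663 | 2.7% | 10.0% |
| 1 | 0 | 3,564 | 0% | 10.0% |

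**Per-protocol set.** If the follow-up exclusion is read more broadly than the Safety set condition, it removes a further share g of the non-completers still present. With f = 0 and no other exclusions, g = 0.5 gives 198/3,762 = 5.3% and g = 0.8 gives 79/3,643 = 2.2%. On the literal wording, the exclusion mostly repeats the Safety set condition and adds little.

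**The case against.** The strongest reply is that few drop-outs may lack safety data. The footnotes to Protocol Table 3.3-1 have immediate reactions recorded for all subjects over 30 minutes after injection. Protocol 7.6 asks only for some safety data, and the table shells of SAP V4.0 carry a 30-minute column. An unreturned Diary Card also triggers telephone contact, with at least three attempts under Protocol 3.3. If the 30-minute record qualifies, the Safety set is almost the Exposed Set and the understatement may be small. This stands as a limit on the size. It does not settle the matter, because the SAP never says what qualifies. The plan also has wording that points the other way: its drop-out allowance is what separates enrolled from evaluable subjects, and Protocol 7.6 ties evaluability to having some safety data.

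Second, Amendment 2 foresees a separate plan for the Korean authority with its own analysis populations. SAP sets that differ from Protocol 7.3 are therefore intended. That is fair, but a disposition table limited to subjects with safety data still does not describe disposition.

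Third, overall shrinkage can be derived from the counts in SAP 7.1, and Protocol 7.6.3 provides a listing of withdrawals due to adverse events. This is true. What remains missing is a completion rate and the other reasons.

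A reader might infer more: that reported attrition is zero in the per-protocol set, or that near-complete follow-up would be shown whatever the true loss. The documents do not support either. Only follow-up loss with unidentifiable safety information is zero by definition, and on the literal wording that holds in both sets. Early leavers with partial data are still counted. Nor is 90% a planned completion rate: the 10% is an allowance from enrolled to evaluable. What a public posting would show cannot be checked, since the shells for section 6.3 are not in the documents I have.

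**Conclusion.** The point holds on the text of the SAP. Section 6.3 restricts termination and reasons to two sets that require safety data, so non-completion is understated whenever at least one drop-out has none. The direction follows from the set definitions; the amount does not. With an assumed 10% non-completion among 3,960, the Safety set figure lies between 10.0% (no understatement) and 0%, and is 5.3% if half of the non-completers lack safety data. That range rests on the borrowed 10% and on an unknown share f. The adverse event analyses themselves are not miscalculated; what is lost is the information needed to judge how complete they are. The change should be made, since it is cheap and the data are already collected.

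**What to change.** In SAP 6.3 and 7.4, give the termination item its own populations: study termination and reason not completed on the All Enrolled Set and the Exposed Set as defined in Protocol 7.3, by age cohort (2 to 23 months; 2 to 55 years). Add these two sets to SAP 3.1. Leave the adverse event items of 6.3 on the Safety and Safety per Protocol sets. One sentence in 3.1 stating whether the 30-minute observation alone counts as post-vaccination safety data would also settle how far the Safety set can differ from the Exposed Set.

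The cost is a few lines of SAP text and one reprogrammed table, using termination data already on the CRF. The reported completion rate may look less favourable.
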